**Intervention Groups and Duration:**

Intervention Groups	This is a multiple dose escalation study using the single agent, modified toxicity probability interval (mTPI) design and will evaluate safety, tolerability, and efficacy in the following treatment interventions:							
Intervention Group Name	Drug	Dose Level	Dose Strength	Dose Frequency	Route of Admin.	Regimen/ Treatment Period/ Vaccination Regimen	Use	
Selumetinib	MK-5618	DL 1	50 mg	BID	Oral	2 weeks on followed by 1 week off	Experimental	
	MK-5618	DL 2	75 mg	BID	Oral	2 weeks on followed by 1 week off	Experimental	
	MK-5618	DL3	100 mg	BID	Oral	2 weeks on followed by 1 week off	Experimental	
	MK-5618	DL4	125 mg	BID	Oral	2 weeks on followed by 1 week off	Experimental	
	MK-5618	DL5	150 mg	BID	Oral	2 weeks on followed by 1 week off	Experimental	
	MK-5618	DL6	200 mg	BID	Oral	2 weeks on followed by 1 week off	Experimental	
	MK-5618	DL7 onwards	Above 200 mg (up to 300 mg)	BID	Oral	2 weeks on followed by 1 week off	Experimental	
Pembrolizumab	MK-3475	DL1-DL7	200 mg	Once every 3 weeks	IV Infusion	Every 3 weeks (Q3W)	Experimental	
Abbreviations: BID = twice daily; IV = intravenous								
Total Number	Based on the emerging safety and/or efficacy signals, an alternate dose level, alternative drug administration frequency and dosing schedule(s) may be explored and an optimal dose will be selected based on totality of data (PK, PD and safety) emerging throughout the trial.							
	There is 1 intervention group (selumetinib + pembrolizumab) in this dose escalation study.							

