## **6.6 Dose Modification (Escalation/Titration/Other)**

### **6.6.1 Dose Modifications Due to Adverse Events**

In previous studies of selumetinib and pembrolizumab monotherapy, overlapping toxicities have been observed for selumetinib and pembrolizumab (refer to IBs). These overlapping toxicities include pneumonitis, diarrhea/colitis, cardiac function decrease, and skin rash.

In the current study, the relationship of these AEs to selumetinib and/or pembrolizumab may be difficult to unambiguously assign. Therefore, if a participant experiences an AE related to either treatment, both selumetinib and pembrolizumab will be modified or discontinued as described in [Table 4](#) and [Table 5](#).

If 2 different therapies are proposed in these tables, the most conservative/effective treatment should be chosen (ie, steroid). Further, if the investigator believes the treatment emergent toxicity is unambiguously related to only one of the agents, they may continue the participant on the unrelated agent following consultation with the Sponsor.

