#### **6.6.1.1 Selumetinib Dose Modification Due to Adverse Events**

The starting dose level for selumetinib is 50 mg BID, and a dose reduction below 50 mg BID is not allowed. Participants requiring additional reductions must discontinue selumetinib treatment.

Missed/skipped doses will not be made up (ie, the participant should not double their dose if the previous dose was missed). When a toxicity results in a dose reduction, the dose cannot be re-escalated.

Dose reduction/interruption/discontinuation decisions should be based on the CTCAE grade of the toxicity and the guidelines provided below. In general, doses should not be reduced or interrupted for Grade 1 toxicities, but treatment to control symptoms should be provided as appropriate.

[Table 4](#) provides dose adjustment recommendations for selumetinib-induced toxicities. During dose interruption the site should consult with the Sponsor regarding the discontinuation and/ or resumption of treatment.

Table 4 Dose Modification Guideline for Selumetinib

Eye disorders- Retinal Events (including serious detachment of the retina)	
Grade 1	Maintain dose level of selumetinib and repeat ophthalmic monitoring including visual acuity assessment and OCT within 10 days.
Grade 2	
Interrupt selumetinib dosing and refer the participant to ophthalmologist within 1 week and obtain OCT within 10 days:
 

• If resolved to baseline or Grade <math>\leq 1</math> within 10 days, resume treatment at current dose level; continue the schedule of visual assessments established per protocol.

• If not resolved to baseline or Grade <math>\leq 1</math> within 10 days, resume treatment at 1 reduced dose level (1 level below that previously received); continue the schedule of visual assessments established per protocol.

• If on retreatment Grade 2 reoccurs, permanently discontinue selumetinib.

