Complicated Grade 1 to 2	Temporarily interrupt selumetinib treatment until resolved to Grade $\leq 1$ . Resume treatment at 1 reduced dose level. If participant is at the lowest dose, participant will be discontinued.
Grade 3 to 4	Temporarily interrupt selumetinib treatment until resolved to Grade $\leq 1$ . Resume treatment at 1 reduced dose level. If participant is at the lowest dose, participant will be discontinued.
Nausea/Vomiting	
Grade 1 to 2	Treatment with selumetinib will be maintained at the current dose. Promptly institute antiemetic measure.
Grade 3	Temporarily interrupt selumetinib treatment until resolved to Grade $\leq 1$ . Resume treatment at the current dose level if, in the judgment of the investigator, the toxicity is considered to be unrelated to selumetinib, or at 1 reduced dose level. Note: Interrupt dose for $\geq$ Grade 3 vomiting or Grade 3 nausea only if the vomiting or nausea cannot be controlled with optimal antiemetics (as per local practice).
Grade 4	Permanently discontinue selumetinib treatment
Interstitial lung disease/pneumonitis	
Grade 1	Maintain dose level of selumetinib. Monitor weekly.
Grade 2	Withhold selumetinib for up to 3 weeks. If improved to Grade 0 or 1, resume treatment at 1 reduced dose level. If not resolved within 3 weeks, permanently discontinue selumetinib.
Grade 3 to 4	Permanently discontinue selumetinib.

Venous Thromboembolism	
Uncomplicated DVT or PE	Withhold selumetinib for up to 3 weeks. If improved to Grade 0 or 1, resume treatment at 1 reduced dose. If not improved, permanently discontinue.
Life threatening PE	Permanently discontinue selumetinib.
All other adverse events (suspected to be related)	
Grade 1 to 2	If the event is a persistent Grade 2 AE not responsive to a specific therapy, consider study drug interruption or reduction.
Grade 3	For other AEs, interrupt study drug until resolution to Grade $\leq 1$ or to pre-treatment/baseline level. If the event resolves within 21 days, then study drug may be resumed at 1 reduced dose level (1 level below that previously received) based upon the investigator's discretion.
Grade 4	Permanently discontinue study drug.

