# **7 DISCONTINUATION OF STUDY INTERVENTION AND PARTICIPANT WITHDRAWAL**

## **7.1 Discontinuation of Study Intervention**

Discontinuation of study intervention does not represent withdrawal from the study.

As certain data on clinical events beyond study intervention discontinuation may be important to the study, they must be collected through the participant's last scheduled follow-up, even if the participant has discontinued study intervention. Therefore, all participants who discontinue study intervention prior to completion of the protocol-specified treatment period will still continue to participate in the study as specified in Section 1.3 and Section 8.10.3.

Participants may discontinue study intervention at any time for any reason or be discontinued from the study intervention at the discretion of the investigator should any untoward effect occur. In addition, a participant may be discontinued from study intervention by the investigator or the Sponsor if study intervention is inappropriate, the study plan is violated, or for administrative and/or other safety reasons. Specific details regarding procedures to be performed at study intervention discontinuation are provided in Section 8.1.9 and Section 8.10.3.

A participant must be discontinued from study intervention but continue to be monitored in the study for any of the following reasons:

- The participant or participant's legally acceptable representative requests to discontinue study intervention.
- The participant interrupts study intervention administration for more than 21 consecutive days during the 3-week cycle.
- The participant has a medical condition or personal circumstance which, in the opinion of the investigator and/or Sponsor, placed the participant at unnecessary risk from continued administration of study intervention.
- The participant has a confirmed positive serum pregnancy test.
- Confirmed radiographic disease progression outlined in Section 8.2 (exception if the Sponsor approves treatment continuation).
- Unacceptable adverse experiences as described in Section 8.3.
- Progression or recurrence of any malignancy, or any occurrence of another malignancy that requires active treatment.
- Intercurrent illness other than another malignancy as noted above that prevents further administration of treatment.
- Investigator's decision to discontinue the participant.
- Recurrent Grade 2 pneumonitis.

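### Table 4's Grade 2 pneumonitis row has no recurrence stop for selumetinib, although Section 7.1 requires stopping study intervention when Grade 2 pneumonitis recurs

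*Combined protocol and SAP*

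**What the plan says.** Section 7.1 states: "A participant must be discontinued from study intervention but continue to be monitored in the study for any of the following reasons". One of the listed reasons is "Recurrent Grade 2 pneumonitis". That bullet sets no condition on attribution and is not confined to one drug. Section 6 defines study intervention broadly enough to take in every investigational product given under the protocol. Table 3 lists selumetinib and pembrolizumab, both as investigational products, and the synopsis says: "There is 1 intervention group (selumetinib + pembrolizumab) in this dose escalation study". Read plainly, the Section 7.1 stop covers both drugs.

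Section 6.6.1 names pneumonitis among the overlapping toxicities of the two drugs and directs that "if a participant experiences an AE related to either treatment, both selumetinib and pembrolizumab will be modified or discontinued as described in" Tables 4 and 5.

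For selumetinib, the Grade 2 pneumonitis row of Table 4 reads: "Withhold selumetinib for up to 3 weeks. If improved to Grade 0 or 1, resume treatment at 1 reduced dose level". The only permanent stop in that row is failure to resolve within 3 weeks.

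Three other rules in Section 6.6.1.1 matter:

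- There is a dose floor: "a dose reduction below 50 mg BID is not allowed. Participants requiring additional reductions must discontinue selumetinib treatment".
- A reduced dose may not be raised again.
- There is a consultation step: "During dose interruption the site should consult with the Sponsor regarding the discontinuation and/ or resumption of treatment".

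Table 5 permanently stops treatment for recurrent Grade 2 pneumonitis. Its action column is headed for pembrolizumab monotherapy, coformulations or IO combinations.

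**The concern.** When pneumonitis occurs, Section 6.6.1 sends the site to the dose-modification tables. At a second Grade 2 event, a site that opens Table 4 finds an instruction to withhold, wait for improvement and resume at a lower dose. Nothing in the row says that a second event is different, and nothing points to Section 7.1, which says that study intervention must stop.

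The row's silence does not look like a convention of the table, because other rows deal with recurrence when that was wanted. The Grade 2 and Grade 3 retinal rows, and the row for CK elevation with renal impairment, stop selumetinib on recurrence. The liver rows reduce the dose, and the rash rows separate first and second occurrences. A reader therefore has no signal that the pneumonitis row covers a first event only.

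What is at stake is participant safety and consistent handling across sites. The protocol treats pneumonitis as a risk of both drugs, says attribution may be difficult, and excludes people with current pneumonitis or a history of non-infectious pneumonitis that needed steroids. A site that followed Table 4 alone could re-expose a participant to selumetinib after a second Grade 2 event and breach Section 7.1 by doing so.

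**Working it through.** The plan gives no figure to reproduce. The check is to step a participant down the dose ladder under Table 4 and compare the result with Section 7.1.

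**Inputs**

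- Fixed selumetinib levels (Section 4.3.1.2): 50, 75, 100, 125, 150 and 200 mg BID, then DL7 onwards, above 200 and up to 300 mg BID.
- Table 4: each Grade 2 pneumonitis that improves to Grade 0 or 1 within 3 weeks costs one dose level.
- Section 6.6.1.1: no reduction below 50 mg BID. If a further reduction is needed, selumetinib stops. There is no re-escalation.
- Section 7.1: stop at the second event, whatever the dose.

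**Assumptions.** One reduced level means the next lower listed level, both events improve within 3 weeks, and no other reduction has taken place.

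**Rule.** The dose after the second event under Table 4 is two levels below the dose at the first event. If no such level exists, the floor stops selumetinib.

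| Dose at first event (mg BID) | After first event | After second event, Table 4 | Second event, Section 7.1 | Same answer? |
|---|---|---|---|---|
| 50 | stopped by floor | no second event on selumetinib | stop | yes |
| 75 | 50 | stopped by floor | stop | yes |
| 100 | 75 | resume at 50 | stop | no |
| 125 | 100 | resume at 75 | stop | no |
| 150 | 125 | resume at 100 | stop | no |
| 200 | 150 | resume at 125 | stop | no |
| above 200 | 200 | resume at 150 | stop | no |

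The last row also assumes that the level below DL7 is 200 mg, because the protocol fixes no intermediate levels there. The two rules part at 4 of the 6 fixed levels and at DL7 onwards.

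**Sensitivity to the step size.** Section 4.3.1.1 speaks of 25 mg increments, while the listed ladder goes from 150 to 200 mg. With plain 25 mg steps, a first event at 200 mg gives 200 - 25 = 175, then 175 - 25 = 150 mg. The lowest first-event dose at which Table 4 resumes selumetinib is 100 mg BID on either reading (100 - 25 - 25 = 50, exactly at the floor).

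**Sensitivity to another reduction.** Suppose one reduction for a different toxicity falls between the two events. Then 100 goes to 75 (pneumonitis) and to 50 (other toxicity), and the floor stops selumetinib at the second pneumonitis. From 125 the path is 100, 75, then resume at 50. The threshold moves up from 100 to 125 mg BID.

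**Could another rule close the gap?** Section 7.1 also stops participants who interrupt for more than 21 consecutive days, but that does not catch an interruption of 21 days or fewer. Section 6.6.1 prefers the more conservative option when the tables propose different therapies. Its example is a steroid, so it does not clearly extend to a dosing decision.

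**The case against.** The strongest reply is that the texts can be read together. Section 7.1 is mandatory and names this exact event. Table 4 is titled a guideline and introduced as recommendations, and it never expressly says to restart after a second event. A careful reader would manage a first event under Table 4 and stop at recurrence under Section 7.1. The Sponsor, who also holds Section 7.1, should be consulted during any interruption. This reply largely stands: Section 7.1 would probably prevail. It does not remove the point, because the protocol states no order of precedence, the row has no cross-reference, and the consultation clause does not say which rule to apply.

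A second reply is that Table 5 already settles the matter, since its heading extends to IO combinations and Section 6.6.1 refers both drugs to both tables. That reading is arguable. Selumetinib is a MEK inhibitor, and Table 4 is the table titled for it, so Table 5 does not clearly reach it. It would be equally wrong to describe Table 5's heading as limited to pembrolizumab alone.

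A reader might infer that the protocol gives two rules of equal standing with opposite answers, or that anyone whose first event was at 100 mg BID or above would be restarted. The documents support neither. The first ignores the difference between a mandatory rule and a guideline. The second ignores the need for recovery within 3 weeks at both events and for no other reduction.

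Section 6.6.1 also lets investigators who are certain that only one agent is to blame act as follows: "they may continue the participant on the unrelated agent following consultation with the Sponsor". That clause applies to adverse events generally and is a side issue here, although it too is not reconciled with the unconditional bullet in Section 7.1.

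**Conclusion.** The point holds as a minor participant-safety inconsistency: Table 4 lacks a recurrence line that Section 7.1 requires. It concerns one event type, and only a second event. Under the stated assumptions the two provisions give different answers for selumetinib when the first event was at 100 mg BID or above, and the same answer at 50 and 75 mg BID.

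The 4-of-6 figure counts dose levels, not participants. The documents give no expected frequency of recurrent Grade 2 pneumonitis, so the number of people affected cannot be estimated. Sponsor consultation may well catch such restarts.

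A reader might also infer that dose finding or the results are compromised. Nothing in the documents supports that, and no effect on escalation decisions, endpoints or sample size is claimed.

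**What to change.** Add one line to the pneumonitis row of Table 4: *Recurrent Grade 2: permanently discontinue selumetinib (see Section 7.1).* A second event would then stop selumetinib at every dose level, in agreement with Section 7.1 and in line with Table 5's rule for pembrolizumab.

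If the sponsor meant only pembrolizumab to stop, the Section 7.1 bullet should instead be limited to pembrolizumab. With either edit, a short clause could say whether the single-agent exception in Section 6.6.1 applies to this event.

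The cost is one line in a table or a few words in one bullet, plus the optional clause. Visits, analyses and sample size do not change.

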Grade 2 AST or ALT ( $>3$ to $5.0 \times \text{ULN}$ ) or $3 \times$ baseline value (if liver metastasis) AND blood bilirubin $\leq 2.0 \times \text{ULN}$	
Interrupt dose of selumetinib until resolved to Grade <math>\leq 1</math> (or Grade <math>\leq 2</math> in case of liver metastasis), then:
 
 
• If resolved in <math>\leq 14</math> days, resume treatment at current dose level and schedule.
 
• If resolved in <math>>14</math> days, resume treatment at 1 reduced dose level.
 
 
Recurrence:
 
 
• Interrupt dosing of selumetinib until resolved to Grade <math>\leq 1</math> (or Grade <math>\leq 2</math> in case of liver metastasis), then resume treatment at 1 reduced dose level.
 

Grade 2 AST or ALT ( $>3$ to $5.0 \times \text{ULN}$ or $3 \times$ baseline value (if liver metastasis) AND blood bilirubin $>2.0 \times \text{ULN}$	
Interrupt dose of selumetinib until resolved to Grade <math>\leq 1</math> (or Grade <math>\leq 2</math> in case of liver metastasis), then:
 
 
• If resolved in <math>\leq 7</math> days, resume treatment at 1 reduced dose level. If not resolved in <math>\leq 7</math> days, permanently discontinue selumetinib.
 

Grade 3 AST or ALT ( $>5.0$ to $8.0 \times$ ULN) AND blood bilirubin $\leq 2.0 \times$ ULN	Interrupt dose of selumetinib until resolved to Grade $\leq 1$ (or Grade $\leq 2$ in case of liver metastasis), then: 
 
• If resolved in <math>\leq 14</math> days, resume treatment at current dose level and schedule.
 
• If resolved in <math>>14</math> days, resume treatment at 1 reduced dose level.
 
 Recurrence: 
 
• Interrupt dosing of selumetinib until resolved to Grade <math>\leq 1</math> (or Grade <math>\leq 2</math> in case of liver metastasis), then resume treatment at 1 reduced dose level.
 

AST or ALT ( $>8 \times$ ULN) AND blood bilirubin* $\leq 2.0 \times$ ULN	Permanently discontinue selumetinib.
AST or ALT ( $>5.0 \times$ ULN) AND blood bilirubin* $>2.0 \times$ ULN	Permanently discontinue selumetinib.
AST or ALT Grade 4 ( $>20.0 \times$ ULN)	Permanently discontinue selumetinib.
Cardiac disorders	

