### 6.6.2.2 Definition of Dose-limiting Toxicity

All toxicities will be graded using NCI CTCAE Version 4.0 based on the investigator assessment. The DLT window of observation will be during first 21-days of treatment.

The occurrence of any of the following toxicities will be considered a DLT, if assessed by the investigator to be possibly, probably or definitely related to study drug administration, excluding toxicities clearly not related to the drug, such as disease progression, environmental factors, unrelated trauma:

1. Grade 4 non-hematologic toxicity (not laboratory).
2. Hematologic toxicity:
  - Grade 4 neutropenia  $>5$  days
  - Grade 4 thrombocytopenia of any duration
  - Grade 3 thrombocytopenia with clinically significant bleeding
  - Other Grade 4 hematologic toxicity lasting  $\geq 7$  days
3. Any non-hematologic AE Grade 3 severity (not laboratory) should be considered a DLT, with the following exceptions:
  - Grade 3 fatigue lasting  $\leq 3$  days
  - Grade 3 diarrhea, nausea, or vomiting lasting  $<72$  hours in the absence of maximal medical therapy
  - Grade 3 rash without use of corticosteroids or anti-inflammatory agents per standard of care
4. Any Grade 3 or Grade 4 non-hematologic laboratory value if:
  - Clinically significant medical intervention is required to treat the participant, or
  - The abnormality leads to hospitalization, or
  - The abnormality persists for  $>1$  week
  - The abnormality results in a Drug-induced Liver Injury (DILI) (see Sections 8.4.1 and 8.4.7 for criteria).

Examples of some exceptions: Clinically nonsignificant, treatable, or reversible laboratory abnormalities include liver function tests, urine acid.

5. Febrile neutropenia Grade 3 or Grade 4:

- Grade 3 is defined as absolute neutrophil count  $<1000/\text{mm}^3$  with a single temperature of  $>38.3^\circ\text{C}$  ( $101^\circ\text{F}$ ) or a sustained temperature of  $\geq38^\circ\text{C}$  ( $100.4^\circ\text{F}$ ) for more than 1 hour.
- Grade 4 is defined as absolute neutrophil count  $<1000/\text{mm}^3$  with a single temperature of  $>38.3^\circ\text{C}$  ( $101^\circ\text{F}$ ) or a sustained temperature of  $\geq38^\circ\text{C}$  ( $100.4^\circ\text{F}$ ) for more than 1 hour, with life-threatening consequences and urgent intervention indicated.

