6. An elevated AST or ALT lab value that is  $\geq3X$  the upper limit of normal and an elevated total bilirubin lab value that is  $\geq2X$  the upper limit of normal and, at the same time, an alkaline phosphatase lab value that is  $<2X$  the upper limit of normal, as determined by way of protocol-specified laboratory testing or unscheduled laboratory testing.
7. Any prolonged delay ( $>2$  weeks) in initiating Cycle 2 study treatment due to a treatment-related toxicity.
8. Any treatment-related toxicity that causes the participant to discontinue treatment during Cycle 1.
9. Missing  $>25\%$  of selumetinib doses as a result of drug-related AE(s) during the first treatment cycle.

10. Grade 5 toxicity

11. Cardiac disorders

- Absolute decrease in LVEF  $>10\%$  compared with baseline and the LVEF is below the institution's lower limit of normal
- Left ventricular systolic dysfunction Grade  $\geq3$
- Other cardiac disorders Grade  $\geq3$

12. Vascular disorders

- Hypertension CTCAE Grade  $\geq3$  requiring more than 1 drug or more intensive therapy
- Grade 4 hypertension

13. Eye disorders

- Retinopathy or retinal detachment Grade  $\geq3$ , confirmed by ophthalmic examination

- Retinal vein disorder including RVO, confirmed by ophthalmic examination
- Visual disturbances without ocular (retinal) changes
- Blurred vision, flashing lights, floaters: Grade  $\geq 3$
- Other (not listed above)
- Grade  $\geq 3$  for  $>21$  consecutive days
- Grade 4 confirmed by ophthalmic examination

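### When Table 4 is followed in Cycle 1, its Grade 4 fallback action plus DLT criterion 8 switches off the duration limits written for short Grade 4 non-platelet cytopenias and some laboratory events

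*Combined protocol and SAP*

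**What the plan says.** **DLT definition (Section 6.6.2.2).** The criteria are alternatives: "The occurrence of any of the following toxicities will be considered a DLT".

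- Criterion 2 counts Grade 4 neutropenia only if it exceeds 5 days. The item beginning "Other Grade 4 hematologic toxicity lasting" requires at least 7 days. Grade 4 thrombocytopenia counts however short it is.
- Criterion 4 counts a Grade 3 or 4 non-hematologic laboratory value only if it needs clinically significant intervention, leads to hospitalization, persists beyond 1 week or amounts to drug-induced liver injury. Its note on exceptions reads: "Clinically nonsignificant, treatable, or reversible laboratory abnormalities include liver function tests, urine acid".
- Criterion 8 counts "Any treatment-related toxicity that causes the participant to discontinue treatment during Cycle 1".
- Criterion 9 counts missing more than 25% of first-cycle selumetinib doses because of drug-related events.

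**Selumetinib dose modification (Section 6.6.1.1, Table 4).** The table has rows for eye, liver, cardiac, CK, rash, diarrhea, nausea/vomiting, lung and venous thromboembolic events, and none for blood counts. The remainder goes to the block headed "All other adverse events (suspected to be related". There a Grade 3 event is interrupted ("If the event resolves within 21 days, then study drug may be resumed at 1 reduced dose level"), and a Grade 4 event leads to "Permanently discontinue study drug". In the liver block, AST or ALT above 8 x ULN with bilirubin at or below 2 x ULN is also a permanent stop. The row headed "AST or ALT Grade 4" starts only above 20 x ULN.

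**The concern.** Criterion 2 treats platelets differently from other cell lines, which shows that brief Grade 4 neutropenia was meant to be tolerated. Table 4 removes that tolerance indirectly: it stops treatment whatever the duration, and criterion 8 then counts the stop. A written limit that cannot take effect invites two classifications of one participant, depending on whether the reader works from criterion 2 or from Table 4 with criterion 8.

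DLTs are a primary endpoint, and the DLT count at the current dose is what is read against Table 1 (Section 4.3.1.4). A de-escalate decision at the lowest dose stops the trial.

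**Working it through.** **1. Tracing each event type.** Assume the event is judged a related adverse event, Table 4 is followed, and action is taken within Cycle 1.

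| Event | Criterion 2 or 4 | Table 4 action | Criterion 8 | Limit still works? |
|---|---|---|---|---|
| Grade 4 neutropenia, 5 days or less | not met | permanent stop (catch-all) | met | no |
| Other non-platelet Grade 4 cytopenia, under 7 days | not met | permanent stop (catch-all) | met | no |
| Grade 4 laboratory event without its own row, no criterion 4 condition met | not met | permanent stop (catch-all) | met | no |
| AST/ALT above 8 x ULN, bilirubin at or below 2 x ULN, no criterion 4 condition met | not met | permanent stop (liver row) | met | no |
| Grade 4 thrombocytopenia | met at once | permanent stop (catch-all) | met | no limit exists |
| Asymptomatic Grade 3 CK, no renal impairment, 1 week or less | not met | dose maintained | not met | yes |
| Asymptomatic Grade 4 CK, no renal impairment, 1 week or less | not met | interrupt, resume one level lower | not met above DL1 | yes above DL1, subject to criterion 9 |
| Other Grade 3 laboratory event in the catch-all, 1 week or less | not met | interrupt, may resume one level lower | not met above DL1 | yes above DL1, subject to criterion 9 |

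In the last two rows, DL1 differs because a reduction below 50 mg BID is not allowed and a required reduction becomes a discontinuation. The first four rows apply at every dose level.

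**2. Criterion 9 and evaluability.** Twice-daily dosing for 14 days (Section 8.1.8.3.1) gives 28 doses in Cycle 1.

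- 25% of 28 = 7, so 8 missed doses meet criterion 9.
- A stop by the end of Day 10 leaves at least 28 - 20 = 8 doses untaken. That is a DLT under criterion 9 whatever criterion 8 says.
- Section 5.6 replaces participants who receive under 75% of selumetinib (fewer than 21 of 28 doses) without a DLT. At 20 of 28 (71%), someone exempted from both criteria would become nonevaluable and be replaced.
- For interrupted events, holds up to 3.5 days miss at most 7 doses. Holds of 4 to 7 days do so only with onset on Day 12 or later.

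**3. Reproducing Table 1.** Inputs are target 0.30, Beta(1,1) prior and epsilon 0.03. For each interval, divide posterior probability by interval length; the largest value gives the decision. Example, 1 DLT in 3, posterior Beta(2,3), with F(p) = 1 - (1-p)^4 - 4p(1-p)^3:

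- F(0.27) = 0.296 and F(0.33) = 0.401
- Escalate: 0.296/0.27 = 1.10
- Stay: (0.401 - 0.296)/0.06 = 1.76
- De-escalate: (1 - 0.401)/0.67 = 0.89

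The decision is S, as printed. With DU taken as posterior P(p > 0.30) above 0.95 (an assumption; the cut-off is not stated), all 78 legible cells in rows 0 to 6 match.

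**4. Effect of one reclassified participant.**

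- n = 3: 0 to 1 DLT is E to S, 1 to 2 is S to D, and 2 to 3 is D to DU. The decision always changes.
- n = 6: 1 to 2 is E to S and 3 to 4 is S to DU. 0 to 1 and 2 to 3 change nothing.
- Across the legible rows, 27 of 66 one-step moves change the decision.

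**5. Illustration with assumed rates (neither is in the documents).** Let p = 0.20 be the rate of other DLTs and q the share of the remainder with such an event found in Cycle 1. The effective rate is r = p + (1 - p)q. At n = 3, P(E) = (1-r)^3 and P(D or DU) = 3r^2(1-r) + r^3. At n = 6, P(E) = (1-r)^6 + 6r(1-r)^5.

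| q | r | P(E), n = 3 | P(D or DU), n = 3 | P(E), n = 6 |
|---|---|---|---|---|
| 0 | 0.20 | 0.512 | 0.104 | 0.655 |
| 0.05 | 0.24 | 0.439 | 0.145 | 0.558 |
| 0.10 | 0.28 | 0.373 | 0.191 | 0.464 |

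**The case against.** **There is no contradiction.** A reader might infer that the plan calls the same event both a DLT and not a DLT. It does not. Any one criterion suffices, and no text says a short Grade 4 cytopenia is not a DLT. Read strictly, criterion 8 settles it, and the error, if any, is toward caution. This stands. What remains is that explicit limits have no effect, and a reader of criterion 2 alone would not know it.

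**Some limits still operate.** A reader might infer that the limits in criteria 2 and 4 can never spare anyone. For criterion 4 that is wrong, as the CK and Grade 3 rows in the working show.

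**Not every Grade 4 value reaches Table 4.** A laboratory result is an adverse event only if the investigator judges it clinically significant (Appendix 3, Section 10.3.1). Table 4 is described as recommendations, and an agent judged unrelated may be continued after Sponsor consultation (Section 6.6.1). These points narrow the reach. But Section 6.6.1.1 also says that decisions should rest on these guidelines, and the default in Section 6.6.1 is that both agents are modified or discontinued. Criterion 8 does not say whether stopping one agent counts, which adds to the ambiguity.

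**Few such events may be seen.** Blood counts are scheduled on Day 1 of each cycle, so brief events may go undetected. Cycle 2 pre-dose laboratory tests may, however, be drawn up to 72 hours early (Section 8.3.7.1), from Day 19 for a Day 22 visit, and unscheduled tests can find others. The frequency is unknown.

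**The liver example is limited.** Table 5 pairs Grade 3 or 4 immune-related AST/ALT elevation with corticosteroids, which may itself satisfy the intervention condition in criterion 4. The example therefore holds only for elevations that meet no criterion 4 condition.

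**Conclusion.** The concern holds within limits. For related Grade 4 neutropenia, other non-platelet Grade 4 cytopenias and Grade 4 laboratory adverse events without their own row, following Table 4 in Cycle 1 triggers criterion 8 and cancels the duration limits of criterion 2 or the conditions of criterion 4. The AST/ALT row above 8 x ULN does the same for short elevations that do not otherwise meet criterion 4. It does not reach Grade 4 thrombocytopenia, asymptomatic Grade 3 CK without renal impairment, or events interrupted and resumed above DL1.

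The firm statement of size is that in a cohort of 3 one such participant always moves the Table 1 decision. The fall in P(E) from 51% to 44-37% rests on the assumed 20% and 5-10% rates and shows scale only. A reader might take it as an estimate of how often escalation would be altered, but the documents give no rate that would support that.

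**What to change.** Reconcile Table 4 (the Grade 4 catch-all action and the AST/ALT row above 8 x ULN) with Section 6.6.2.2, so that one rule decides whether a short Grade 4 cytopenia or laboratory adverse event in Cycle 1 is a DLT. No view is taken here on which clinical rule should stand; that is for the sponsor. The amendment should:

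- treat criteria 2, 4, 8 and 9 together, since a change to criterion 8 alone leaves any stop by the end of Day 10 a DLT under criterion 9;
- state how the 75% rule in Section 5.6 applies to a participant who stops early for an event that is not counted;
- state whether stopping one agent counts as discontinuing treatment under criterion 8;
- delete the duration limits that cannot operate, if every such event is meant to count.

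The cost is a few sentences by amendment, with no extra participants or tests.
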